#### 5.0 STUDY CALENDAR

#### **Pre-study Testing Intervals:**

The pre-study testing intervals are guidelines only. Laboratory and clinical parameters during treatment are to be followed using individual institutional guidelines and the best clinical judgment of the responsible physician. It is expected that patients on this study will be cared for by physicians experienced in the treatment and supportive care of patients on this trial.

When calculating days of tests and measurements, the day a test or measurement is done is considered Day 0. Therefore, if a test were done on a Monday, the Monday one week later would be considered Day 7.

	Prior to Registration	Baseline booklets (Days 1-7)	Daily during treatment (Days 8-49)	End of each week of treatment
Tests & Observations				
History and physical, including Vital signs	Х			
Height, Weight, ECOG PS	X			
Baseline Symptom Documentation ( Appendix II )		X (1)		
International Prostate Symptom Score- (Appendix III)	X			Х
Hot Flash Diary ( Appendix IV )			Х	
Symptom Experience Questionnaire ( Appendix V )		A (1)		Х
Hot Flash Related Daily Interference Scale (HFRDIS) ( Appendix VI )		A (1)		B(2)
Telephone Contact and AE assessment (Appendix VII)				X (2)

**To be completed** ≤ **60 DAYS before registration:** History and physical.

1 Nurse/research coordinator should call the patient, to remind him to send in the baseline questionnaire booklets to the site, which are required to be completed prior to start of study treatment.

- 2 All patients will receive weekly phone calls from study staff (nurse or research coordinator), to document compliance with study drug, encourage completion of patient questionnaires, assess adverse events, and address any patient concerns or problems. They will also remind the patient to return the completed questionnaire booklets. For patients who choose to cross over, nurse phone calls will occur weekly to assess adverse events during the unblinded cross over phase. (See Section 7.3)
- A To be completed on Day 7.
- B To be completed at the end of Weeks 2, 4 and 6 only (Weeks 3, 5 and 7 when measured from registration).

#### 6.0 DATA SUBMISSION

#### 6.1 Data Collection and Submission

#### 6.1.1 Data submission schedule

A Data Submission Schedule (DSS) is available on the Alliance study webpage, within the Case Report Forms section. The Data Submission Schedule is also available on the CTSU site within the study-specific Case Report Forms folder.

#### 6.1.2 Medidata Rave

Medidata Rave is a clinical data management system being used for data collection for this trial/study. Access to the trial in Rave is controlled through the CTEP-IAM system and role assignments.

Requirements to access Rave via iMedidata:

- A valid CTEP-IAM account; and
- Assigned a Rave role on the LPO or PO roster at the enrolling site of: Rave CRA, Rave Read Only, Rave CRA (LabAdmin), Rave SLA, or Rave Investigator.

Rave role requirements:

- Rave CRA or Rave CRA (Lab Admin) role must have a minimum of an Associate Plus (AP) registration type;
- Rave Investigator role must be registered as an Non-Physician Investigator (NPIVR) or Investigator (IVR); and
- Rave Read Only role must have at a minimum an Associates (A) registration type.

Refer to for registration types and documentation required.

This study has a Delegation of Tasks Log (DTL). Therefore, those requiring write access to Rave must also be assigned the appropriate Rave tasks on the DTL.

Upon initial site registration approval for the study in Regulatory Support System (RSS), all persons with Rave roles assigned on the appropriate roster will be sent a study invitation email from iMedidata. To accept the invitation, site staff must either click on the link in the email or log in to iMedidata via the CTSU members' website under *Data Management* > Rave Home and click to *accept* the invitation in the *Tasks* pane located in the upper right corner of the iMedidata screen. Site staff will not be able to access the study in Rave until all required Medidata and study specific trainings are completed. Trainings will be in the form of electronic learnings (eLearnings) and can be accessed by clicking on the eLearning link in the *Tasks* pane located in the upper right corner of the iMedidata screen. If an eLearning is required for a study and has not yet been taken, the link to the eLearning will appear under the study name in the *Studies* pane located in the center of the iMedidata screen; once the successful completion of the eLearning has been recorded, access to the study in Rave will be granted, and a *Rave EDC* link will replace the eLearning link under the study name.

Site staff that have not previously activated their iMedidata/Rave account at the time of initial site registration approval for the study in RSS will receive a separate invitation from iMedidata to activate their account. Account activation instructions are located on

the CTSU website in the Data Management section under the Rave resource materials (Medidata Account Activation and Study Invitation Acceptance). Additional information on iMedidata/Rave is available on the CTSU members' website in the Data Management > Rave section at \_\_\_\_\_\_ or by contacting the CTSU Help Desk at \_\_\_\_\_\_ or by email at \_\_\_\_\_\_ or by email at \_\_\_\_\_\_\_

#### 6.1.3 Data Quality Portal

The Data Quality Portal (DQP) provides a central location for site staff to manage unanswered queries and form delinquencies, monitor data quality and timeliness, generate reports, and review metrics.

The DQP is located on the CTSU members' website under Data Management. The Rave Home section displays a table providing summary counts of Total Delinquencies and Total Queries. DQP Queries, DQP Delinquent Forms, DQP Form Status and the DQP Reports modules are available to access details and reports of unanswered queries, delinquent forms, forms with current status and timeliness reports. Review the DQP modules on a regular basis to manage specified queries and delinquent forms.

The DQP is accessible by site staff that are rostered to a site and have access to the CTSU website. Staff that have Rave study access can access the Rave study data using a direct link on the DQP.

To learn more about DQP use and access, click on the Help icon displayed on the Rave Home, DQP Queries, DQP Delinquent Forms, DQP Form Status, and DQP Reports modules.

#### 6.2 Submission of Patient Completed Measures

Patient-completed questionnaire booklets for this study are to be ordered prior to the registration of any patients (see Section 4.3). Samples of questionnaire booklets are available in Appendices I-VII for reference and IRB submission only. They are not to be used for patient completion. Booklets must be given to patients to complete and patients should be instructed to return the booklets to site staff either in person or by mail and site staff will enter patient responses into Medidata Rave. At visits in which booklets are to be completed, the booklet should be given to the patient before any discussion of the patient's health status or test results. The PRO submission schedule is provided in the Study Calendar.

Weekly Booklets: Six booklets to be completed weekly must be given to patients to complete at home and patients should be instructed to return the booklets by mail weekly or to return the booklets at their regularly scheduled clinic visit. Institutions must provide patients with sufficient self-addressed stamped envelopes for this purpose. Site staff will enter patient responses into Rave upon receipt of the completed booklets.

Verbal administration of the measures for visually impaired patients is permitted if the verbal administration of the measure is conducted in a language understandable to the patients.

#### 6.2.1 Patient Language Considerations

The patient reported measures are available in English. Participation in Alliance A222001 is restricted to patients who are able to speak, understand and read English. Ad-hoc translation of patient-completed measures is not permitted.

#### 7.0 TREATMENT PLAN/INTERVENTION

#### Protocol treatment is to begin $\leq 8$ days of registration.

For questions regarding treatment, please see the study contacts page.

This is a randomized, double-blind trial. The pharmacist or designated contact (see Section 4.6) at the institution will be informed of the patient's randomization, so that they may prepare oxybutynin or placebo for delivery to the patient (see Section 10.0).

The placebo arms will be half the size as the oxybutynin arms, as they will be combined to have a placebo group with the same number of patients as the two different dose groups. This allows all patients to be blinded as to whether they are receiving active drug or a placebo.

Patients will be assigned to one of the following treatment groups, and continue to receive treatment for 6 weeks (i.e., 42 days):

	Days 1-7	Days 8-49
Oxybutynin 2.5 mL	Patients on all arms will be	Oxybutynin 2.5 mL* PO twice a day
Placebo 2.5 mL	asked to complete questionnaires as baseline	Placebo 2.5 mL* PO twice a day
Oxybutynin 5 mL	symptom documentation on Days 1-7, before starting	Oxybutynin 5.0 mL* PO twice a day
Placebo 5.0 mL	study treatment on Day 8.	Placebo 5.0 mL* PO twice a day

\* Note that the concentration of oxybutynin is 1 mg per 1 ml, so that placebos and active treatments will maintain blinding.

Upon completion of the 6-week study period, patients will be contacted to ensure they have completed all required questionnaires.

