#### 3.2 Eligibility Criteria

Use the spaces provided to confirm a patient's eligibility by indicating Yes or No as appropriate. It is not required to complete or submit the following page(s).

When calculating days of tests and measurements, the day a test or measurement is done is considered Day 0. Therefore, if a test were done on a Monday, the Monday one week later would be considered Day 7.

- **3.2.1** Men who are currently receiving androgen deprivation therapy (ADT) for the treatment of prostate cancer. ADT is defined by a history of orchiectomy, or ongoing usage of gonadotropin-releasing hormone agonists or antagonists. Men receiving abiraterone, but not enzalutamide, apalutamide, and darolutamide are eligible, as the latter three are metabolized by CYP3A4 and may affect oxybutynin serum concentrations.
- **3.2.2** Patients must be on a stable dose of all hormone-directed therapies for at least 28 days prior to registration and must not be planning to discontinue this therapy for at least 42 days following registration.

Patients receiving radiation therapy during the study period are eligible.

- 3.2.3 Eligible patient must have bothersome hot flashes for  $\geq$  14 days prior to registration, defined by an occurrence of  $\geq$  28 times per week and of sufficient severity to cause the patient to seek therapeutic intervention.
- 3.2.4 No current use or future planned use of any of the following agents during the study period: drugs that are not FDA approved for use in humans, drugs with category X interactions with oxybutynin [e.g. other anti-cholinergic agents, eluoxadloline, and potassium chloride], androgens, estrogens, progesterone analogs, gabapentin, cholinergic agonists, cholinesterase inhibitors, or complementary/alternative medicine taken for the purpose of managing hot flashes. No current or future planned use of strong CYP3A4 inhibitors (e.g. antipsychotic agents or macrolide antibiotics) during the study.

Prior use of these agents is permitted as long as they are discontinued before registration.

3.2.5 No current or prior use of oxybutynin for the treatment of hot flashes. Prior use of oxybutynin for other purposes (e.g. bladder symptoms) is allowed, as long as the patient has not taken any oxybutynin for 30 days prior to registration.

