#### **10.0 DRUG INFORMATION**

#### **10.1** Oxybutynin Chloride Oral Syrup (Ditropan)

#### IND: Alliance A222001 uses Oxybutynin under an Alliance IND.

#### Procurement

Oxybutynin Chloride 5mg/5 mL oral syrup (473 mL) and ORA-Sweet® Solution (473 mL) stock bottles will be provided and shipped by McKesson Clinical Research Services to sites.

After receiving IRB approval for this study, each participating institution will order a starter supply of three bottles of oxybutynin oral syrup and two bottles of ORA-Sweet® solution from McKesson Clinical Research Services by faxing or emailing the Alliance Clinical Drug Order/Return Form to:

The A222001 Oxybutynin/Placebo Order Form can be found on the A222001 study page of the Alliance and CTSU websites.

Each site is responsible for monitoring their inventory and ordering additional bottles as needed. Each site will provide their own 16 oz. amber bottles.

Sites are also expected to provide each patient with an oral syringe to measure and take their medication, along with instructions for rinsing and reusing it for the duration of the study.

Main member institutions will be provided a per patient reimbursement by the Alliance for their rebottling services and supplies.

Within ninety days after the last patient is treated at the institution, any expired or remaining supplies should be destroyed according to institutional procedure.

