#### Availability

Oxybutynin oral syrup is available as 5 mg/5mL concentration with raspberry flavor. The solution contains citric acid, D&C Yellow No 10, FD&C Blue No 1, glycerin, liquid sugar, methylparaben, propylene glycol, sodium citrate, and sorbitol solution.

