#### 10.2 Placebo Oral Solution

#### Procurement

Please see ordering instructions in Section 10.1, for both active agent and placebo.

The placebo for this study will be ORA-Sweet® SF and ORA-Sweet® · ORA-Sweet® SF and ORA-Sweet® are a berry citrus flavored inert syrup vehicle. The ORA-Sweet® SF contains purified water, sorbitol, sodium saccharin, xanthan gum, and flavoring. It is buffered with citric acid and sodium phosphate, and preserved with methylparaben, propylparaben, and potassium sorbate. ORA-Sweet® SF contains FD&C Red#40 and is sugar-free and alcohol-free. ORA-Sweet® contains purified water, sucrose, glycerin, sorbitol, and flavoring. It is buffered with citric acid and sodium phosphate, and preserved with methylparaben and potassium sorbate.

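### Equal concentration matches the volume of active and placebo but not their listed dyes and flavours, and Sections 10.1 and 10.2 disagree on which placebo product is used

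*Combined protocol and SAP*

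**What the plan says.** **Basis given for blinding.** The note under the treatment table in Section 7.0 says that "the concentration of oxybutynin is 1 mg per 1 ml, so that placebos and active treatments will maintain blinding". The schema page carries the same note.

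**Active product.** Under Availability, Section 10.1 says: "Oxybutynin oral syrup is available as 5 mg/5mL concentration with raspberry flavor". The ingredients that follow include "D&C Yellow No 10, FD&C Blue No 1".

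**Placebo product.** Section 10.2 names two products, ORA-Sweet SF and ORA-Sweet, which "are a berry citrus flavored inert syrup vehicle". Of the first it says that it "SF contains FD&C Red#40 and is sugar-free and alcohol-free". The second is sucrose based and no dye is listed for it. In Section 10.1, the ordering, preparation and drug accountability paragraphs mention ORA-Sweet only.

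**Other safeguards.** Section 4.6 requires a common label and bars the unblinded preparer from assessing adverse events or any other outcome. Section 10.1 uses an amber bottle and a label that names both possibilities. Section 7.0 provides a placebo arm for each volume.

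**Handling and endpoint.** "Sites are also expected to provide each patient with an oral syringe to measure and take their medication" (Section 10.1; Appendix VIII repeats it for the patient). The type of syringe is not stated. Under Section 13.3, hot flash scores come from the patient's diary.

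**The concern.** Section 7.0 credits equal concentration with maintaining the blind, but concentration settles only how many millilitres a man takes. Colour and taste depend on the other ingredients, and the lists for active and placebo differ in both dye and flavour. No section available for this review says that the liquids are matched for colour, taste or viscosity.

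The other safeguards work on the bottle and on the site preparer. The person who administers the dose is the patient. He looks at the liquid in the syringe and tastes it, and he also supplies the primary outcome as counts and severity ratings, which expectation can influence.

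The disagreement between Sections 10.1 and 10.2 adds a further uncertainty. If both placebo products were dispensed, placebo men would differ from one another in dye and sweetener. The plan has no item on perceived assignment. Question 23a in Appendix V asks about expected benefit, and only at baseline.

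**Working it through.** **1. The listed properties side by side**

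| Property | Active (10.1) | ORA-Sweet (10.2; also supplied under 10.1) | ORA-Sweet SF (10.2 only) |
|---|---|---|---|
| Volume per dose | 2.5 or 5 mL | 2.5 or 5 mL | 2.5 or 5 mL |
| Flavour | raspberry | berry citrus | berry citrus |
| Listed dye | yellow and blue | none listed | red |
| Sweetening | liquid sugar | sucrose | sugar-free, with saccharin |

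Only volume is matched by concentration. For the product that Section 10.1 supplies, the contrast is a dyed active syrup against a placebo with no dye listed. Two different dyes are at issue only if SF is used. The documents do not state the resulting colour of any of the three liquids.

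**2. Where each safeguard applies**

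- Common label, amber bottle and separated preparer: up to the point where the liquid leaves the bottle.
- Matched placebo volumes: these hide the arm as far as volume goes.
- Syringe and mouth: no stated safeguard. Exposures per man: 42 days × 2 doses = 84.

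**3. What a bias would do (illustration)**

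The documents give neither a correct-guess rate nor an effect of expectation, so both are assumptions here.

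The plan's own figure first. Section 13.5 gives 76% power for 26 versus 26 with d = 0.50, intraclass correlation 0.50, six weekly scores and two-sided alpha 0.10. The SD factor for a six-week mean is √((1 + 5 × 0.50)/6) = 0.764. Then 0.50/(0.764 × √(2/26)) = 2.36, and the normal probability at 2.36 − 1.645 gives 76.3%, or 75.3% with the t distribution on 50 df. The stated figure reproduces and is not in dispute.

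Now take the same t-test with no drug effect and a bias of b SD between the arms. The chance of p < .10 in one comparison is:

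| b | six-week-mean variance | single week-6 score |
|---|---|---|
| 0 | 10% | 10% |
| 0.1 | 13.7% | 12.1% |
| 0.2 | 24.3% | 18.5% |
| 0.3 | 40.3% | 28.5% |

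For one possible anchor, Section 1.2 quotes a placebo-arm change of −5.7 (SD 10.2) and a 5.0 mg change of −16.9 (SD 15.6) in women. Suppose that 20% to 40% of men in both arms infer their arm and that knowing it is worth the full 5.7 points.

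- Spurious difference: 0.2 × 5.7 = 1.14 to 0.4 × 5.7 = 2.28 points.
- SD of change: √((15.6² + 10.2²)/2) = 13.2.
- In SD units: 1.14/13.2 = 0.09 to 2.28/13.2 = 0.17, against the planned 0.50.
- Chance of p < .10 for 26 versus 26 with that SD of change: about 12% to 16%.

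The 5.7 points is the whole change from baseline in a placebo arm. It would include regression to the mean and natural course, so it does not estimate the effect of knowing one's arm.

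**The case against.** The strongest reply is that a difference is not recognition. The design is parallel, and each man has one sweet, berry-type syrup under a label that fits either content. Without something to compare it with, colour and flavour tell him nothing. This stands, and it limits the finding.

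The routes to an outside reference are narrow. Section 3.2.5 says that "Prior use of oxybutynin for other purposes (e.g. bladder symptoms) is allowed" after 30 days off drug, but it does not say that the earlier product was the syrup, and no figure is given for how many such men would enrol. The package insert is made available to investigators and research staff (Section 10.1), and no section available for this review gives men an ingredient list.

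It is also fair that the note in Section 7.0 sits under a table in millilitres and may only be explaining why the volumes match, and that Section 4.6 adds real safeguards. But those safeguards do not reach the drawn-up dose, and the note as worded claims more than matched volume.

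A reader might infer that men will be unblinded, or that a positive result could not be defended. The documents support neither: they give no guess rate, no expectation effect and no actual colours. Nor do they say that the syringes are clear, or that SF is ever dispensed. The patient information sheets (Appendix IX) were not in the text available for this review, so a statement on matching there cannot be excluded.

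**Conclusion.** The point holds as a gap in the blinding provisions and a contradiction between sections. It does not show that the blind fails. Three things follow directly from the text: concentration matches volume only; the listed dye and flavour of the active syrup differ from those of either placebo product; and Section 10.2 names two placebo products where Section 10.1 supplies one. The safeguards leave the measured dose uncovered in a trial whose primary endpoint is self-reported.

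The size of any bias is unknown. Under the assumptions in the working it would be 0.09 to 0.17 SD, about one-fifth to one-third of the planned 0.50. The false-positive chance of one comparison would then move from 10% to about 12% to 16%. Larger inflation, such as 24% to 40%, needs an assumed bias of 0.2 to 0.3 SD on the six-week-mean variance, and nothing in the documents supports a bias of that size. The change is worth making because it is cheap, not because harm has been shown.

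**What to change.** 1. Reconcile Sections 10.1 and 10.2 so that ordering, preparation, accountability and product description name one placebo product for all placebo men.
2. Specify amber or opaque oral syringes in Section 10.1. Sites already supply a syringe, so only the type changes.
3. Reword the note in Section 7.0 and on the schema page to say that equal concentration matches volume, and that flavour and dye are not matched.

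Optional: add one item to the week-6 booklet asking which treatment the man believes he received and why. Sections 4.7 and 7.3 already require the questionnaires to be complete before unblinding, so the answer would come in time. Guesses will partly reflect efficacy or dry mouth, so the item would help interpretation only and should not be used to adjust the result.

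Cost: a small amount per patient for syringes and some protocol wording. Flavour stays unmatched, so the risk is reduced and not removed. A further instruction to keep telephone staff from seeing the liquid would add little, because weekly adverse event assessment is by phone and the preparer is already separated from assessment.

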#### 7.1 Baseline Symptom Documentation

The patient will be instructed not to take any study medication for the first seven days of the study, but to complete their daily questionnaires (Baseline Symptom Documentation – Appendix II) during this baseline period. At the end of the week, patients will complete Symptom Experience Questionnaire (Appendix V) and Hot Flash Related Daily Interference Scale (Appendix VI).

#### 7.2 Oxybutynin/Placebo

Beginning on Day 8 of the study, and for the subsequent six weeks, patients will be instructed to take their study medication as illustrated below.

- Oxybutynin: 2.5 mL oral BID Days 8 through 49 (total of 42 days)
- Placebo: 2.5 mL oral BID Days 8 through 49 (total of 42 days)
- Oxybutynin: 5.0 mL oral BID Days 8 through 49 (total of 42 days)
- Placebo: 5.0 mL oral BID Days 8 through 49 (total of 42 days)

